2.5 Blinding

This is a double-blind study with limited access to the randomization code. Tildrakizumab and placebo will be identical in physical appearance. The treatment each subject will receive will not be disclosed to the Investigator, study center staff, subject, Sponsor, or study vendors. The treatment codes will be held by the Clinical Supplies Department of the Sponsor or their designated Contract Research Organization (CRO).

| Effective Date: 10-AUG-2020 | Page 15 of 61 |
|-----------------------------|---------------|

All subjects will be dosed at the same time points to maintain the study blind throughout the study. Returned study treatment should not be re-dispensed to the subjects.

3 DATA ANALYSIS CONSIDERATIONS

3.1 General presentation of Summaries

Descriptive statistics (number [n], mean, standard deviation [SD], median, minimum [min], and maximum [max]) for continuous variables and frequency and percentages for discrete variables will be utilized. All summaries and analyses conducted will be by assigned therapy and/or combined total subjects, where appropriate. Data obtained on the eCRF and entered into the database will be provided in data listings showing individual subject values. Unless otherwise noted, the data listings will be sorted first by treatment assignment, subject number and then by date within each subject number.

| Effective Date: 10-AUG-2020 | Page 16 of 61 |
|-----------------------------|---------------|

For summary statistics, the mean and median will be displayed to one decimal place greater than the original value and the measure of variability (i.e., SD) will be displayed to two decimal places greater than the original value.

All tabulations of summary statistics, graphical presentations, and statistical analyses will be performed using SAS® Version 9.4 or higher.

3.2 Definition of Baseline Values

Unless otherwise specified, "Baseline" is defined as the last observed value of the parameter of interest prior to the first intake of study treatment (this includes unscheduled visits).

For Nail Pain NRS, the complete observation will be performed on the average score for each visit that will be based on the seven daily scores. The complete score at a given visit will be based on an average of no less than four of the seven prompted valid daily recall observations. No imputation of missing daily recalls will be used, and the change in averaged scores at Baseline and Week 28 will provide the basis for analysis. Hence, baseline NRS will be defined as the average score of the 7 consecutive daily scores leading up to the Baseline Visit (Visit 2); the baseline score will be computed if there are four or more valid scores out of the seven prompted assessments. If a subject missed 4 or more entries during the 7 days before Baseline visit, the Baseline NRS value will be considered as undefined (missing) for the subject.

For numerical variables, change from Baseline will be calculated as the difference between the post-Baseline value and the corresponding Baseline value and calculated as: post-Baseline value — Baseline value. The percent change from Baseline will be calculated as change from Baseline divided by the Baseline value, expressed as a percentage.

3.3 Analysis Time points

Unless specified otherwise, efficacy and safety endpoints will be analyzed according to their scheduled study visits; unscheduled and early termination visits will be mapped to windowed analysis visits defined by actual study day as in table 1.1 below. If there is no evaluation available from the scheduled study visit, and more than one non-missing evaluation is assigned to an analysis window, the evaluation closest to the target day will be used for the analysis. If the two visits are equidistant from the target day, the earlier visit will be used. For early terminated patients, Part 3 is to start the day of last assessment after the last injection plus 28 days.

The following analysis visit windows will apply:

Table 1.1 Analysis Visit Windows

For: ViSENPsO, NAPSI, mNAPSI, PGA-S, BSA, PASI, and C-SSRS

| Derived Visit | Week | Target Day | Analysis Window |
|---|------|------------|-----------------|
| Part 1: Double-blind Placebo-controlled | | | |

| Effective Date: 10-AUG-2020 | Page 17 of 61 |
|-----------------------------|---------------|

| | _ |
|--|---|
| | |

| _ | |
|-----------------------------|---------------|
| Effective Date: 10-AUG-2020 | Page 18 of 61 |

In particular, NRS pain score will be recorded daily in patient diary for the 7 days leading up to each scheduled visit. The analysis visit for NRS will be assigned the same as for the subsequent visit according to Table 1.1, ie, as 7 consecutive days prior to that visit. In the event of a missed visit, the available NRS scores will be mapped to an analysis visit according to Table 1.1, using the last diary entry date as anchor. Any NRS entries outside of the 7-day window will be excluded from the calculation of average NRS. At least 4 out of the 7 daily records are required to calculation of average.

All other assessments (ECG, laboratory data) will be analyzed according to the assigned (nominal) visit unless otherwise specified.

[figure not shown]
For any events/assessments on or after the first administration of study drug, study day is calculated as: event/assessment date – date of first administration of study drug + 1. As such, Day 1 is defined as the date of first administration of study drug.

For any events/assessments before the first administration date, study day is calculated as event/assessment date – date of first administration of study drug.

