This is a multicenter, randomized, double-blind, placebo-controlled study to assess the efficacy and safety of tildrakizumab in the treatment of moderate to severe psoriasis of the nails.

Subjects with a clinical diagnosis of chronic plaque psoriasis for at least 6 months and moderate to severe psoriasis of the nails at screening and baseline (mNAPSI score of \geq 20, ViSENPsO of \geq 3, and PASI \geq 12) as well as moderate to severe plaque psoriasis at screening and baseline (s-PGA score of at least \geq 3, and BSA involvement of \geq 10%) and who are considered candidates for systemic therapy will be enrolled in the study.

After a screening period of 28 days, all eligible subjects will be randomly allocated (in a 1:1 ratio after stratification according to previous use of TNF-alpha inhibitors [yes/no] and baseline body weight [≤90 kg or >90 kg]) on Day 1 to receive either tildrakizumab 100 mg or placebo by subcutaneous (SC) injection on Week 0 (Day 1), 4, and 16. Subjects should receive the first dose of study treatment within 24 hours of randomization.

At Week 16, subjects who experience significant worsening of plaque psoriasis (defined as an increase in s-PGA by at least 2 from the baseline measurement) will be eligible for an early escape. Subjects selected for early escape by the Principal Investigator at Week 16 will have study medication discontinued and will complete the End of Treatment visit assessment, followed by the observational safety follow-up period. Subjects entering early escape may be replaced to meet the planned evaluable sample size goal for the primary endpoint analysis.

At Week 28, subjects initially randomized to placebo will be switched over to receive tildrakizumab 100 mg at Weeks 28, 32, and 44. Subjects initially randomized to tildrakizumab 100 mg will continue to receive tildrakizumab at Weeks 28, 40, and 52. In order to maintain the blind, subjects in both treatment arms will receive matching placebo injections at specified time points as described in the Schedule of Assessment (SoA).

Subjects who experience significant worsening of plaque psoriasis at Week 28 (defined as an increase in s-PGA by, at least 2 from the baseline measurement) will be discontinued from treatment. Subjects who do not fulfill this criterion at Week 28 will continue to receive tildrakizumab in Part 2, as described above.

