7.0 DISCONTINUATION OF STUDY TREATMENT AND SUBJECT DISCONTINUATION/WITHDRAWAL

7.1 Discontinuation of Study Treatment

Subjects may voluntarily discontinue study treatment for any reason at any time and enter the 20-week wash-out period or completely withdraw from the study (see Section 7.2). Subjects who consent to enter the wash-out period will undergo the Week 52 (EoT) assessment at approximately 4 weeks after administration of the last dose of study treatment.

At any time during Part 1 or Part 2 of the study, the Investigator should discontinue the study treatment of a given subject if, on balance, he/she believes that continuation would be detrimental to the subject's well-being.

The study treatment must be discontinued under the following circumstances, and the further steps need to be discussed with the Medical Monitor:

- An SAE, drug reaction or complication, or an unacceptable AE, whether attributed to study treatment or not, precludes the continuation of treatment with study treatment. This includes the development of allergic reactions or the development of other potentially serious drug reactions to medication required by the protocol.
- Diagnosis of malignancy (except basal or squamous cell carcinoma of the skin) during the study (at the discretion of the subject and Investigator).
- Meets early escape criteria at week 16 or week 28
- Subjects who develop suicidal behavior.
- Evidence of pregnancy.
- Withdrawal of informed consent.
- Lost to follow-up.
- Significant non-compliance of the subject with study procedures.
- Decision of the Sponsor to terminate the subject, study center, or the study.

Subjects who discontinue the study treatment may not be replaced.

Subjects who withdraw from the study will undergo the assessment that corresponds to the end assessment of the study part which they are leaving. Week 52 assessments (EoT) should be conducted approximately 4 weeks after administration of the last dose of study treatment.

See the SoA (see Section 1.3) for data to be collected at the time of treatment discontinuation and follow-up and for any further evaluations that need to be completed.

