7.2 Subject Discontinuation/Withdrawal from the Study

Subjects may voluntarily withdraw consent to participate in the study for any reason at any time.

Withdrawal of consent occurs when a subject does not want to participate in the study anymore and does not want to attend any further visits or assessments, have further study-related contact, or allow an analysis of already obtained biologic material.

If a subject withdraws consent, the Investigator must make every effort to determine the primary reason for this decision and record this information on the treatment disposition eCRF page. If the subject decides to completely withdraw from the study (refuses any further study participation or contact), all study participation for that subject will cease, and data to be collected at subsequent visits will be considered missing. The study treatment must be discontinued, and no further assessments will be conducted. Further attempts to contact the subject are not allowed unless safety findings require communication or follow-up.

However, for safety reasons, Week 52 (EoT) assessments should be conducted for subjects withdrawing during Part 1 or 2, if the withdrawn subject is willing to undergo the assessments. For subjects withdrawing during Part 3 and willing to undergo final assessments, the Week 72 (EoS) assessments should be conducted approximately 4 weeks after their last visit.

The appropriate personnel from the study center and CRO will assess whether the study treatment should be discontinued for any subject whose treatment code has been broken inadvertently for any reason.

The Investigator must also contact the IWRS to register the subject's discontinuation from the study treatment.

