After Week 52 (or early termination of study treatment prior to Week 52), the study treatment should be stopped and all subjects, including those who terminated early from Part 1 and 2 will enter the 20-week Observational Safety Follow-up period to monitor safety and tolerability for 20 weeks following the last dose of study treatment. During the follow-up period, subjects should continue on study-approved concomitant medications only, however, may be placed on appropriate therapies for safety concerns or significant worsening of

| Effective Date: 10-AUG-2020 | Page 10 of 61 |
|-----------------------------|---------------|

psoriasis based on the judgment of the Investigator. The subjects will not receive study treatment during the follow-up period.

Subjects who withdraw from the study will undergo the assessment that corresponds to the last assessment of the study part from which they are leaving. Subjects discontinued from study treatment at any time (apart from withdrawal of informed consent) will complete the EoT (Week 52) assessment approximately 4 weeks after the last dose of study treatment and enter the 20-week Observational Safety Follow-up. Subjects who withdraw from the study during Part 3 will undergo the Week 72 (End of Study [EoS]) assessments approximately 4 weeks after their last visit.

All assessments of safety in PART 3 are scheduled to happen after the date of injection at Week 52. The analysis of efficacy and safety endpoints for PART 3 will follow the analysis visit window and definitions as specified in the sections below.

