10.2 Clinical Laboratory Evaluation

Absolute values and changes from Baseline of clinical laboratory data (hematology, chemistry, continuous urinalysis parameter, and lipids) will be summarized with descriptive statistics at Baseline, and Week 28 (i.e., Part 1, and through Week 52 and Week 72 for the final analysis. For the laboratory values which have the normal range (e.g., below/within/above the normal range) or categorical result (e.g., ¬/±/+), a shift table will display the cross tabulation of the Baseline result category versus the result of the post-treatment period at each visit according to the study part being reported.

All clinical laboratory data relevant to the reporting period (i.e., Part 1 or overall) will be listed by subject. Values outside the normal ranges will be flagged. Flags will describe direction relative to normal range in relevant parameters.

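### Because laboratory data stay on their nominal visit, draws taken when a subject stops treatment in Part 1 miss the Part 1 laboratory summaries as written

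*SAP*

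**What the plan says.** **Visit assignment (SAP 3.3).** As the general rule, "unscheduled and early termination visits will be mapped to windowed analysis visits defined by actual study day as in table 1.1". The heading of that table names ViSENPsO, NAPSI, mNAPSI, PGA-S, BSA, PASI and C-SSRS. Laboratory data are not named and get their own rule: "All other assessments (ECG, laboratory data) will be analyzed according to the assigned (nominal) visit unless otherwise specified". The same section adds: "For early terminated patients, Part 3 is to start the day of last assessment after the last injection plus 28 days".

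**Visit at stopping treatment.** Under SAP 2.1, a subject taken off treatment for any reason other than withdrawn consent "will complete the EoT (Week 52) assessment approximately 4 weeks after the last dose of study treatment". Early escape at Week 16 leads to the same visit: in the Protocol synopsis such subjects "will have study medication discontinued and will complete the End of Treatment visit assessment".

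**Visit at leaving the study.** Protocol 7.1 says: "Subjects who withdraw from the study will undergo the assessment that corresponds to the end assessment of the study part which they are leaving". Protocol 7.2 says instead that "Week 52 (EoT) assessments should be conducted for subjects withdrawing during Part 1 or 2", provided the subject is willing.

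**Laboratory summaries (SAP 10.2).** Laboratory values "will be summarized with descriptive statistics at Baseline, and Week 28 (i.e., Part 1"; Weeks 52 and 72 are added for the final analysis. Shift tables are by visit. All values for the reporting period are listed by subject, with out-of-range values flagged.

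**Sampling (Protocol 1.3).** Hematology and chemistry are scheduled at Screening, Baseline and Weeks 28, 52 and 72.

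**The concern.** Part 1 is the only placebo-controlled period, and Week 28 is its only scheduled post-baseline laboratory visit. For a subject who stops treatment earlier, the EoT draw is the first scheduled post-baseline sample. If it carries a Week 52 label, the subject adds nothing after baseline to the one laboratory comparison made against placebo.

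The omission may be related to the outcome. Protocol 7.1 requires treatment to stop for an unacceptable adverse event, and Appendix 3 counts a clinically significant laboratory abnormality as an adverse event. SAP 10.1 places adverse events in Part 1 by date, so an event could appear in the Part 1 table while the laboratory value behind it appears elsewhere.

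The Week 52 row is also affected. By then, continuing placebo subjects have received tildrakizumab since Week 28, whereas a placebo subject who stopped in Part 1 has received none.

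**Working it through.** **1. The plan's own figures.** Protocol 9.2 gives 43 evaluable and 48 randomized per arm. With 35% against 10%, two-sided alpha 0.05, 80% power and a pooled Z-test:

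n = [1.960 × √(2 × 0.225 × 0.775) + 0.842 × √(0.35 × 0.65 + 0.10 × 0.90)]² / 0.25² = 42.6, so 43 per arm.

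43 / 0.90 = 47.8, so 48. Both figures reproduce. They serve here only to bound the number of subjects; this point does not contest them.

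**2. When the stopping draw happens.** Part 1 doses are at Weeks 0, 4 and 16 (SAP 2.1), and EoT is about 4 weeks after the last dose. Study day = 7 × week + 1.

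| Last dose | EoT draw | Study day | Weeks before nominal Week 52 |
|---|---|---|---|
| Week 0 | Week 4 | 29 | 48 |
| Week 4 | Week 8 | 57 | 44 |
| Week 16 | Week 20 | 141 | 32 |

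Week 28 is Day 197, so all three draws fall inside Part 1 by date.

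**3. Where the rules send it.** The general rule in SAP 3.3 yields where something else is specified, and the laboratory sentence does specify something else. The draw therefore keeps its nominal visit, and the row depends on the route and the label:

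| Subject | Label | Row in SAP 10.2 |
|---|---|---|
| Stops treatment, stays in study (including early escape) | EoT (Week 52) | Week 52, not Part 1 |
| Same, if the eCRF has a separate early-termination visit | Early termination | None |
| Withdraws from study, Protocol 7.1 followed | Week 28 | Part 1 |
| Withdraws from study, Protocol 7.2 followed | EoT (Week 52) | Week 52 |

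**4. How many.** The planning allowance is 48 − 43 = 5 per arm, or 5/48 = 10.4%. At assumed rates of 5% to 15%, the count is 48 × 0.05 = 2.4 to 48 × 0.15 = 7.2 per arm. Each figure is a ceiling for its rate: some subjects who drop out have no draw, and some carry a Week 28 label. Early escape adds few. Entry needs s-PGA of at least 3 (Protocol 5.1), the scale stops at 5 (Appendix 20) and escape needs a rise of at least 2, so only a move from 3 to 5 qualifies.

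**5. What a few values could do (illustration; counts assumed).** Suppose 2 of 43 completers are abnormal at Week 28 in each arm, a reported difference of 0. Suppose also that 1 or 2 tildrakizumab stoppers and no placebo stoppers are abnormal.

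- All 5 stoppers per arm sampled: 3/48 − 2/48 = 2.1 points, or 4/48 − 2/48 = 4.2 points.
- Only 2 of 5 sampled: 3/45 − 2/45 = 2.2 points, or 4/45 − 2/45 = 4.4 points.

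**The case against.** The strongest reply is that a by-visit table always omits subjects without that visit. SAP 4.1 analyses safety as observed cases, and the rule in SAP 10 that summaries use the whole safety set fixes a population, not a visit. That is right, so the Week 28 row itself is not wrong. It does not answer the absence of any other Part 1 summary that picks up these draws, or their placement in a Week 52 row.

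Second, much is covered elsewhere. SAP 10.2 lists and flags the values, and Protocol 9.4.2.2 promises summaries of clinically significant changes and of treatment-emergent abnormal values. This reduces the impact. But listings give no comparison between arms, and the visible SAP 10.2 does not carry the Protocol's promise into a Part 1 table.

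Third, the label is inferred. The eCRF is not available, the body of Table 1.1 is not legible, SAP 12, 15 and 16 were not supplied, and the laboratory rule allows exceptions. An exception cannot be excluded, though the explicit laboratory sentence makes one in Table 1.1 unlikely.

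Three stronger readings are tempting, and the documents do not support them:

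- *That Protocol 7.1.1 shows laboratory abnormalities drive the omission.* That section covers temporary interruption. A subject who resumes treatment has no early EoT draw and can be sampled at Week 28.
- *That Protocol 9.5 already puts these draws in the Week 28 analysis by date.* Its date limit is worded for subjects who complete Part 1.
- *That a difference of 2 to 4 points is being hidden.* Those figures rest on assumed counts, with every abnormal stopper placed in one arm.

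**Conclusion.** The point holds on the visible text for subjects who stop treatment in Part 1 and remain in the study. Their EoT draw, at about Week 4, 8 or 20, is left out of the Part 1 summaries and by-visit shift tables. It joins the Week 52 row or falls in none. For study withdrawers, the row depends on which Protocol section the site follows.

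The size is modest. At most about 5 of 48 per arm are affected on the planning figure, and probably fewer. The data are descriptive and remain in the listings; no efficacy test or sample size changes. That the omission depends on outcome is a possibility, resting on Protocol 7.1 with Appendix 3, and is not shown. The conclusion assumes that no exception sits in the text not supplied. It merits a correction to the SAP, but it does not threaten the trial.

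**What to change.** In SAP 3.3, assign laboratory results from EoT, early-termination and unscheduled draws to study part by date. Part 1 would run to the Week 28 injection, or to Day 210 where there is none, borrowing the limit in Protocol 9.5 and stating that it applies to subjects who stop early. Keep Part 1 draws out of the Week 52 row. State one visit label for subjects who withdraw from the study in Part 1.

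In SAP 10.2, keep the Week 28 row and add a Part 1 shift from baseline to worst post-baseline value using all Part 1 draws. SAP 10.6 already plans a worst-post-baseline shift for C-SSRS. Use the same draws for the treatment-emergent abnormal values in Protocol 9.4.2.2.

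The cost is SAP wording and one further table from data already collected. The drawback is that the added table mixes draw times, so it supplements the Week 28 row and does not replace it.

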3.4 Protocol Deviations

All protocol deviations (PD) will be tracked throughout the study and classified by deviation type, either minor or major. Protocol deviations represent a failure to adhere to the clinical study protocol. The two types of deviations are defined as:

- Minor protocol deviation is any change, divergence, or departure from the study
 design or procedures of a research protocol that has not been approved by the IRB and
 which does not have a major impact on the subject's rights, safety or well-being, or
 the completeness, accuracy and reliability of the study data.
- Major protocol deviation is any change, divergence, or departure from the study
 design or procedures of a research protocol that has not been approved by the IRB or
 which has a major impact on the subject's rights, safety or well-being, or the

Prior to primary analysis database freeze and final database lock, each deviation will be reviewed to determine if it excludes the patient from any of the analysis sets or any particular

| Effective Date: 10-AUG-2020 | Page 19 of 61 |
|-----------------------------|---------------|

planned analysis. These determinations will then be described in the relevant clinical study report. Deviations that result in exclusion of subjects from the Per Protocol Set (PPS) will be presented in a listing. Minor protocol deviations will be presented as well. All deviations will be retained within the deviations tracker (considered the source document).

Protocol deviations attributable to the COVID-19 pandemic regardless of whether deemed major or minor will be provided in a separate listing by study parts (i.e., Parts 1, 2, 3) if deemed necessary.

